11 OTHER PLANNED ANALYSES

11.1 AGREEMENT WITH MMSE AND RBANS ANALYSES

Linus Platform individual tests will be compared to MMSE and RBANS to measure agreement in assessment of cognitive status in the Evaluable Population. Additionally, Linus Platform individual tests will be combined to obtain a Linus overall score (Linus score) to measure cognitive status: the training dataset will be used to create a Linus score based on the individual Linus Platform tests and the Evaluable Population will be used to validate the Linus score by assessing its agreement with MMSE and RBANS. I.e., all analyses below will be carried out on the Evaluable Population.

Since most of the Linus Platform tests are administered twice (once at visit 1 and once at visit 2), the RBANS is administered twice (at visit 1 and visit 2) and the MMSE is only administered once (at visit 1) the following sets of comparisons will be made:

1. MMSE at Visit 1 vs. Individual Linus Platform Score or Developed Linus Score at Visit 1
2. RBANS at Visit 1 vs. Individual Linus Platform Score or Developed Linus Score at Visit 1
3. RBANS at Visit 2 vs. Individual Linus Platform Score or Developed Linus Score at Visit 2

For each pairing of the individual Linus Platform scores or the developed Linus score and the reference standard MMSE and RBANS (Reference score), agreement analyses will be carried out as follows:

- Linus scores will be standardized by taking the subject's Linus score, subtracting by the overall Linus score mean and dividing by the overall Linus score standard deviation. This method will also be used to standardize the MMSE scores and RBANS scores. To better visualize the relationship between the two tests, the standardized Linus score will be plotted separately against a standardized reference score (either MMSE or RBANS) in a scatter plot, superimposed with a line of identity.
- Linear and rank linear regression analyses will be conducted and p-values with 95% CI will be calculated for the y-intercept and slope of each model. Either the Pearson (linear regression) or the

Spearman (rank regression) correlation coefficients will be produced and superimposed onto the scatter plots for each regression method, along with 95% CIs and the estimated regression line. In these regressions, the dependent variables are either the individual Linus Platform score or the developed Linus scores and the independent variables are either the MMSE scores or the RBANS scores.

In addition to above, descriptive statistics (N, mean, standard deviation, median, minimum, maximum) for the MMSE score, RBANS score, Linus total score and the Linus Platform individual test scores will be presented by visit and overall.

Figures will display the above described plots.

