## 7.3.4 SCHEDULE OF EVENTS TABLE

Procedure	Screening/Visit 1	Visit 2
Time	Day 0	Within 3-5 weeks of visit 1
Consent	X	
Inclusion/Exclusion Criteria	X	X
Medical History/Demographics	X	
MMSE	X*	
Hamilton-Veale Contrast Sensitivity	X	
Purdue Peg Board	X	
Brief Neurological Assessment	X	
DCTclock Test (either digital pen or tablet version)	X	X
Linus Platform drawing tests	X	X
Linus Platform decision making and reaction time assessments	X	X^ &
Linus Platform lifestyle questionnaire		X
Linus Platform gait and balance assessment	X	X
RBANS	X	X
Linus Platform speech elicitation assessments	X#	X
Linus Platform eye tracking-based memory assessments		X
Assessment of adverse device effects	X	X

\*- MMSE not administered if a LAR consents to the study due to a documented prior MMSE or MoCA score of  $\leq 18$

 PHQ-9 depression screen is included in the decision making and reaction time assessments on visit 2 only

^ reaction time only is assessed twice on visit 2

#- List learning only is combined with the drawing tests on visit 1. All speech and voice assessments are given on visit 2.

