**Exploratory endpoints:**

- Linus Platform tests individual and combined agreement with MMSE and RBANS assessment of cognitive status. Study data will be split into training and testing subsets, with the training subset used to create a Linus overall score based on the individual Linus Platform tests and the testing subset used to validate the Linus overall score and each individual Linus test score by assessing their agreement with MMSE and RBANS.
- Test-retest reliability of both individual Linus Platform tests and the combined Linus overall score compared to the test-retest reliability of the RBANS.

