**10.3 DESCRIPTION OF STATISTICAL METHODS****10.3.1 GENERAL APPROACH**

All subjects will undergo testing with DCTclock-tablet, DCTclock-pen, Linus Platform tests, and RBANS. The DCTclock analysis algorithm generates an overall score (DCTclock score) of performance on the test, as well as a set of Composite Scales: Drawing Efficiency, Information Processing, Simple and Complex Motor, and Spatial Reasoning. The training dataset will be used to both adjust the DCTclock analysis algorithm and create Linus Platform algorithms. The validation dataset will be used to validate the DCTclock equivalence and Linus Platform test endpoints. Descriptive statistics will be measured on both the overall score and the composite scales. There will be no imputation of missing data. Statistical tests will be performed using two-sided significance levels of 5% unless otherwise specified. Statistical analysis will be conducted with R version 3.6 or higher.

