#### 10.3.4 EXPLORATORY ENDPOINTS

##### 10.3.4.1 AGREEMENT WITH MMSE AND RBANS

Linus Platform individual tests will be compared to MMSE and RBANS to measure agreement in assessment of cognitive status in the validation dataset. Additionally, Linus Platform individual tests will be combined to obtain a Linus overall score (Linus score) to measure cognitive status: the training dataset will be used to create a Linus score based on the individual Linus Platform tests and the validation dataset will be used to validate the Linus score by assessing its agreement with MMSE and RBANS.

For each pairing of the individual Linus Platform scores or the developed Linus score and the reference standard MMSE and RBANS (Reference score), agreement analyses will be carried out as follows:

- To better visualize the relationship between the two tests, the Linus score and will be plotted separately against the Reference score in a scatter plot, superimposed with a line of identity.
- Linear and rank linear regression analyses will be conducted and p-values with 95% CI will be calculated for the y-intercept and slope of each model. Either the Pearson (linear regression) or the Spearman (rank regression) correlation coefficients will be produced and superimposed onto the scatter plots for each regression method, along with 95% confidence intervals and the estimated regression line.

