6.2 EVALUABLE POPULATION

The evaluable population for this study includes all ITT subjects who undergo cognitive testing with both DCTclock-pen and DCT-clock table and the Linus Platform tests. Given that no initial tablet model needs to be trained, the evaluable population is the primary analysis population for effectiveness.

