6.4 TRAINING POPULATION

The training population consists of subjects from the evaluable population that were not selected for the validation population.

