12 SUMMARY OF CHANGES FROM THE PROTOCOL

The following table provides a list of changes from the protocol to the SAP, and the justification for each change.

Section	Description	Justification
7.1 Analysis Software	Added SAS® Software version 9.4 or later (the protocol only specifies R version 3.6 or later)	This will allow for programmers to use either SAS or R for analyses

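### SAP 11.1 validates the trained Linus score on a population that is about 71% training data, an undeclared departure from the protocol's held-out validation

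*SAP*

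**What the plan says.** Protocol section 10 (exploratory endpoints) splits the data, with "the testing subset used to validate the Linus overall score and each individual Linus test score". Protocol 10.3.1 repeats the rule: "The validation dataset will be used to validate the DCTclock equivalence and Linus Platform test endpoints". Protocol 10.3.4.1 applies it to this analysis: "the validation dataset will be used to validate the Linus score by assessing its agreement with MMSE and RBANS".

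SAP 11.1 keeps the first half of that design, since the score is still created on the training data. It changes the second half: "the Evaluable Population will be used to validate the Linus score by assessing its agreement with MMSE and RBANS". It then confirms that every analysis in the section uses the Evaluable Population. SAP 6.4 defines the training set: "The training population consists of subjects from the evaluable population that were not selected for the validation population". SAP 6.3 fixes the Validation Population at 50 evaluable subjects drawn at random.

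The reason for moving to the larger population is in SAP 6.2: "Given that no initial tablet model needs to be trained, the evaluable population is the primary analysis population for effectiveness". The SAP document history gives the same reason at version 0.4. SAP section 12 opens with "The following table provides a list of changes from the protocol to the SAP, and the justification for each change", and its only entry is about software. In SAP Appendix A, the shell for the MMSE, RBANS and Linus descriptives is still headed Validation Population.

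**The concern.** A score tested on the subjects who determined its weights looks better than it would in new subjects. By definition the training set lies wholly inside the set SAP 11.1 uses for validation, and no held-out assessment of the Linus score remains in the plan.

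The stated reason does not reach this analysis. If no tablet model is trained, the DCTclock equivalence analysis can use all evaluable subjects without leakage. The Linus score, however, is still trained in this study.

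Aim 3 is to obtain data for developing and validating the Linus tests, and SAP 11.1 is the only planned comparison of the developed score with MMSE and RBANS. If weights or test selection are tuned to either reference, or to a correlate, the correlations, slopes, p-values and confidence intervals reported as validation are partly in-sample.

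**Working it through.** **1. Overlap.** Inputs: 175 evaluable subjects anticipated (Protocol 4.1; SAP section 2); Validation Population of 50 (SAP 6.3); Training = Evaluable minus Validation (SAP 6.4).

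- Training size: 175 − 50 = 125. This split meets the plan's own targets (SAP section 4) of at least 100 for training and more than 41 for validation.
- Training share of Evaluable = (N − 50)/N: 125/175 = 71.4%. If 150 are evaluable, 100/150 = 66.7%; if 200, 150/200 = 75.0%.
- Under the protocol's rule the overlap is 0/50 = 0%.

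**2. Number of inputs to the score.** SAP 3.2.3 lists 20 tests. At Visit 1 there are 5 drawing tests, 3 reaction-time tests, gait and balance, and one speech task (Protocol 7.3.4: "List learning only is combined with the drawing tests on visit 1"), so 5 + 3 + 1 + 1 = 10. All 20 are available only at Visit 2, where RBANS is the only reference.

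**3. Size of the optimism.** The plan gives no figure for this analysis, so the following are assumptions: one sub-score per test; p independent standard normal sub-scores with equal true weights; ordinary least squares fitted to the reference on 125 subjects; residual variance p(1 − R²)/R² for non-zero R². Mean correlation over 3,000 simulated trials of 175:

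| Inputs p | True R² | Training 125 | Evaluable 175 | Held-out 50 | 5-fold out-of-fold |
|---|---|---|---|---|---|
| 10 | 0 | 0.277 | 0.195 | −0.001 | −0.035 |
| 10 | 0.25 | 0.551 | 0.521 | 0.446 | 0.434 |
| 10 | 0.50 | 0.732 | 0.717 | 0.678 | 0.674 |
| 20 | 0.25 | 0.605 | 0.544 | 0.396 | 0.393 |
| 20 | 0.50 | 0.758 | 0.726 | 0.646 | 0.644 |

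As a hand check, the Evaluable value is close to the size-weighted mean of the training and held-out values. For p = 10 and R² 0.25: (125 × 0.551 + 50 × 0.446)/175 = 91.175/175 = 0.521.

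A repeat with 1,500 replicates agreed to within 0.01. For p = 5 it gave 0.507 against 0.469 at R² 0.25, and 0.713 against 0.692 at R² 0.50.

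**4. Where the gap shrinks.**

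- A second reference the score was not fitted to (residual correlation with the fitted one assumed 0.3 to 0.6, p = 10): Evaluable against held-out 0.468 to 0.492 against 0.442 to 0.446 at R² 0.25; 0.691 to 0.703 against 0.674 to 0.678 at R² 0.50.
- An equal-weight composite built without the reference, at R² 0.25: 0.501 against 0.497, which is no material optimism.

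**5. Price of a hold-out.** Fisher interval tanh(atanh r ± 1.96/√(n − 3)) at r = 0.45: n = 50 gives 0.196 to 0.647; n = 175 gives 0.323 to 0.561.

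**The case against.** The strongest reply is that the endpoint is exploratory, has no success threshold, and gains precision from using everyone. In the same model with 10 inputs, root mean squared error around the score's true correlation is 0.091 in Evaluable against 0.118 in the held-out 50 at R² 0.25, and 0.052 against 0.078 at R² 0.50. A biased estimate from 175 can therefore beat an unbiased one from 50. That stands as an argument against relying on the 50 alone, although at 20 inputs and R² 0.25 it reverses (0.154 against 0.119). It does not defend SAP 11.1, because out-of-fold scoring beats both at 10 inputs (0.075 and 0.046).

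The SAP can also say the change was disclosed. Version 0.4 of its history records modified exploratory analyses, and SAP sections 2 and 3.2.3 openly name the evaluable set for individual-test agreement. That is a fair point on openness, but none of it gives a reason that covers a score still being trained, and section 12 omits the change.

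Two limits on size also stand. SAP 11.2 needs the developed score at both visits, so a common score has at most 10 inputs; the 20-input rows apply only to a separate Visit 2 score against RBANS. A score fitted to one reference shows the full gap only for that reference.

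For individual tests whose scoring was fixed beforehand, using Evaluable causes no leakage. There the matter is only an unlisted departure from the protocol. Protocol 10.3.1 does, however, allow Linus algorithms to be created on the training data.

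**Conclusion.** The concern holds. The overlap (71.4% at 175 evaluable) and the conflict with protocol sections 10, 10.3.1 and 10.3.4.1 follow from the documents' own definitions and need no assumption.

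The bias is conditional. It arises if the Linus score is fitted to MMSE, RBANS or a correlate, which neither document states or rules out. Under the 10-input least-squares assumption it inflates the mean correlation by about 0.07 at R² 0.25 and 0.04 at R² 0.50. For a reference not used in fitting, the inflation is about 0.02 to 0.05. With no true association, a correlation of about 0.20 would appear where the true value is zero. More than one feature per test would widen the gap; a fixed or unsupervised composite would remove it, leaving only the undeclared departure and the unspecified method.

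Primary equivalence and safety conclusions are not touched. The point should be fixed because the plan would report training data as validation.

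**What to change.** In SAP 11.1:

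- Assess the developed Linus score against MMSE and RBANS using cross-validated out-of-fold scores for all evaluable subjects, with any test selection and tuning repeated inside each fold. Alternatively, use the Validation Population only, as the protocol does.
- State the fitting method and the training target.
- Label any full-Evaluable result for the developed score as including training data.

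Elsewhere in the SAP:

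- Align the Appendix A descriptives shell with the population chosen.
- Enter in section 12, with a justification, every remaining departure from protocol sections 10 and 10.3.4.1. This includes out-of-fold scoring, if adopted, and individual tests analysed on Evaluable.

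The cost is SAP wording and some programming, with no new data. Restricting to the 50 widens the interval as shown above. Out-of-fold scoring largely avoids that and is slightly conservative (0.434 against 0.446 held out at 10 inputs and R² 0.25).

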STUDY DESIGN	Randomized crossover trial consisting of two test visits separated by a washout period of 3 to 5 weeks. Subjects are randomized into two equal groups. Group 1 receives the digital pen (DCTclock-pen) version of the test at the first visit, with the tablet version (DCTclock-tablet) given at the second visit; Group 2 receives DCTclock-tablet at the first visit, followed by DCTclock-pen at the second visit. At Visit 1 (Day 0), eligibility is assessed and a version of the DCTclock test is administered based on the group allocation. A battery of Linus Platform tests and reference standard tests are also administered. At Visit 2 (Day 21-35), eligibility is assessed and the alternate version of the DCTclock test is administered based on the group allocation. A battery of Linus Platform tests is also administered, together with reference standard tests. Equivalence of DCTclock-pen and DCTclock-tablet will be tested. Linus Platform test data will also be collected to develop novel measures of cognitive and motor function and assess their accuracy in detecting impairment, construct validity, and test-retest

	
reliability. 200 subjects will be recruited to participate with the anticipation that 175 will be available for analysis.

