7.2 DISPOSITION OF SUBJECTS AND WITHDRAWALS

All subjects who were screened will be accounted for. The number of subjects who were screened, eligible, in the ITT Population, in the Evaluable Population, in the Validation Population, in the Training Population, and in the Safety Population will be presented by randomized group (tablet-pen vs. pen-tablet) and overall (both randomized groups combined). The number and percent of ITT subjects who attended visit 1 and who attended visit 2 will be presented by randomized group and overall. This by-visit breakdown will be repeated for the Evaluable and Safety Populations.

The number and percent of ITT subjects prematurely withdrawing will be presented overall, by timing of withdrawal (during first visit, after first visit and before second visit, during second visit) and by reason for withdrawal (Subject did not want to complete this testing session; Subject did not want to return for a second testing session; Subject did not show up for scheduled testing session and could not be reached for rescheduling within the time window; PI felt that it was not in the best interest of the subject to continue in the study; Subject met exclusion criteria during visit 2; None given; Other) for each randomization group and overall.

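### SAP 11.1 makes the two Visit 1-only Linus agreement comparisons conditional on a Visit 2 clock test they do not use, dropping between 0% and 12.5% of usable subjects on the plan's 200/175 figures

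*SAP*

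**What the plan says.** SAP 11.1 lists three comparisons. The first is "MMSE at Visit 1 vs. Individual Linus Platform Score or Developed Linus Score at Visit 1" and the second is "RBANS at Visit 1 vs. Individual Linus Platform Score or Developed Linus Score at Visit 1". The third pairs RBANS and Linus scores at Visit 2. One population rule covers all three: "I.e., all analyses below will be carried out on the Evaluable Population".

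SAP 6.2 defines that population as one that "includes all ITT subjects who undergo cognitive testing with both DCTclock-pen and DCT-clock table and the Linus Platform tests". In the crossover each subject takes one clock version at Visit 1, and at Visit 2 "the alternate version of the DCTclock test is administered based on the group allocation" (SAP 2, Study Design). A subject without a Visit 2 clock therefore cannot be evaluable.

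SAP 7.2 foresees such subjects. Its withdrawal reasons include "Subject did not want to return for a second testing session", no-shows, and meeting an exclusion criterion at Visit 2. SAP 7.3 says they are not replaced and that nothing is imputed. SAP 11.1 plans no supporting analysis on everyone with Visit 1 data.

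The planning figures are in SAP 2: "200 subjects will be recruited to participate with the anticipation that 175 will be available for analysis". Protocol 5.3 describes the 200 as the number screened. Under Protocol 7.3.1, screen failures stop before the Linus tests and RBANS.

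**The concern.** Requiring both clocks is right for pen-tablet agreement, which needs the pair. Comparisons 1 and 2 need no pair and nothing from Visit 2. A subject who changes a listed medication after Visit 1, for example, is excluded at Visit 2, but that does not invalidate the scores already recorded. The SAP gives no reason for carrying the rule over.

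Two things are at stake. The first is precision, because usable Visit 1 pairs are set aside. The second is selection, because Visit 1 agreement is estimated in a group defined by a later event, return for the Visit 2 clock. The study sets out to recruit a range of cognitive function (Protocol 5.3). If more impaired subjects return less often, the range narrows and the correlation is attenuated. Whether the regression slope is also affected depends on what drives non-return.

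**Working it through.** **Inputs.** 200 recruited (SAP 2) or screened (Protocol 5.3); 175 anticipated analysable (SAP 2). The documents state no dropout rate and do not split the difference.

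**1. The plan's own figure.** 200 − 175 = 25, and 25/200 = 12.5%. In reverse, 175/(1 − 0.125) = 200, so the figures are consistent. The denominator is people recruited or screened, not people with Visit 1 scores.

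**2. Share of subjects with Visit 1 scores who are dropped.** Let x be the number of screen failures among the 200, and assume the other 25 − x are lost after a complete Visit 1. The share is (25 − x)/(200 − x).

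| x (assumed) | With Visit 1 scores | Dropped | Share |
|---|---|---|---|
| 0 | 200 | 25 | 12.5% |
| 5 | 195 | 20 | 10.3% |
| 10 | 190 | 15 | 7.9% |
| 15 | 185 | 10 | 5.4% |
| 20 | 180 | 5 | 2.8% |
| 25 | 175 | 0 | 0% |

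**3. Precision at the maximum (x = 0).** The Fisher-z standard error is 1/√(n − 3).

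- n = 175: 1/√172 = 0.0762
- n = 200: 1/√197 = 0.0712
- Reduction: 1 − √(172/197) = 6.6%

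For an assumed r of 0.50, the 95% interval is 0.380 to 0.604 at n = 175 and 0.388 to 0.597 at n = 200.

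**4. Selection, under an assumed dropout model.** Reference and Linus scores were simulated as bivariate normal with true r = 0.60, both with SD 1, so the true slope of Linus on reference is also 0.60. Non-return was set at 12.5% overall, with log-odds rising by 1 or 2 per SD of worse score. Correlation and slope were recomputed in those who return.

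| Non-return depends on | Correlation | Slope |
|---|---|---|
| Reference score alone | 0.56 to 0.58 | 0.60 (unbiased) |
| Standardised combination of both scores | 0.53 to 0.57 | 0.53 to 0.57 |

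The slope is unbiased in the first row because SAP 11.1 makes the reference score the independent variable, and selection on the independent variable alone leaves the regression intact. This holds on the original score scale. If both scores are re-standardised within the selected sample, the slope equals the correlation and is attenuated with it.

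**The case against.** The strongest reply is that little turns on this. The endpoints are exploratory, with no success criterion and no power target, and the interval barely moves. One population also keeps comparisons 2 and 3 and the test-retest analysis in SAP 11.2 on the same people. The restriction is inherited too: Protocol 10.3.4.1 used a 50-subject validation subset of the same Evaluable dataset, so the SAP already enlarges the sample. All of this is correct. It bears on how much the point matters, but gives no reason for a Visit 1 comparison to require a Visit 2 clock. A common-population result can be kept as a sensitivity analysis.

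The selection argument is also open to challenge. Nothing in the documents links return to cognition, and the dropout slopes are assumed. That stands, and the figures show only what could happen.

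A reader might infer two stronger points that the documents do not support.

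- **That 12.5% of subjects with complete Visit 1 data are discarded.** Screen failures have no Linus or RBANS data, so 12.5% applies only if none of the 200 fails screening. Nor is it a firm ceiling. The sample size section speaks of about 175 enrolled, with at least 100 for training and more than 41 for validation. Read as a minimum of 142 evaluable, that would allow a loss of 33/175 = 18.9%.
- **That non-returners, who lie outside the Training Population, should be pooled with the 50-subject Validation Population to enlarge a held-out set.** SAP 11.1 validates on the whole Evaluable Population, not on those 50. Unweighted pooling would also make non-returners up to 25/75, or one third, of the set, against at most 12.5% of the cohort. Under the dropout model above, that inflates a true correlation of 0.60 to about 0.62 to 0.65.

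**Conclusion.** The concern holds in a limited form. Comparisons 1 and 2 are conditioned on a Visit 2 test they do not use, and subjects with the needed Visit 1 scores are dropped as a result. On the 200/175 figures the share is 0% to 12.5%, and the documents do not allow it to be narrowed. The precision cost is at most 6.6% of the standard error on those figures.

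The possible attenuation, from 0.60 to between 0.53 and 0.58 for the correlation, rests on assumed 12.5% non-return that depends on cognition. The slope is affected only if non-return depends on the Linus score as well as, or instead of, the reference score. Comparison 3 and the primary endpoint are untouched. This is an inexpensive improvement to exploratory analyses and does not threaten the trial's main conclusion.

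**What to change.** In SAP 11.1, run comparisons 1 and 2, and the Visit 1 columns of the descriptive table, on all ITT subjects who have the two Visit 1 scores that the comparison requires, whether or not they attended Visit 2. Define the required scores per comparison: MMSE is not given to some subjects consented by a legally authorized representative, and most speech tasks, PHQ-9, the lifestyle questionnaire and eye tracking are given only at Visit 2 (Protocol 7.3.4).

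Keep the Evaluable Population for comparison 3, and report comparisons 1 and 2 on it as a sensitivity analysis. Footnote the differing Ns. Do not add Visit 1-only subjects to a held-out validation subset.

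Correct the descriptive table shell in Appendix A at the same time. It is headed Validation Population, which disagrees with the text of SAP 11.1.

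The cost is a short edit to SAP 11.1, the shell heading and footnotes. No new data are needed. The only drawback is that Visit 1 and Visit 2 comparisons will rest on different numbers of subjects.
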